1. BACKGROUND AND RATIONALE

Socio-economic position (SEP) has a key-role in health and several studies have highlighted differences in dietary behaviour between people of lower and higher SEP as potential mediators of this relationship [1]–[3]. It has been shown that people of lower SEP are more likely to behave in ways that increase the likelihood of developing cardiovascular diseases and obesity (e.g., higher consumption of meat and fatty foods, alcohol consumption and smoking) [4], [5]. In developed countries, the prevalence of obesity and other chronic diseases has dramatically increased within all the socio-economic groups [6] but to a larger extent among poorer and less educated groups [7]. This social gradient might be explained by lower SEP being associated with increased energy intake [8]–[10].

Nutritional labelling is one of the most common intervention that has been implemented to reduce energy intake [11]. Nutritional labels provide consumers with different types of information (e.g. nutritional composition, energy content) in various ways (e.g. numerical, daily recommended intake, traffic lights) and may have a positive impact on food choices and energy intake [11]. However, Sarink et al. (2016) investigated the impact of kcal labelling in people of lower vs. higher SEP and showed that it may benefit more people of higher SEP than people of lower SEP, which may in turn increase health inequalities [12].

A novel form of labelling is Physical Activity Calorie Equivalent (PACE) which may be an alternative to numerical energy labelling [13]. PACE labelling aims to encourage healthier eating behaviours by providing an interpretation of the energy content of a food in terms of energy expenditure: how many minutes (time) or how many kilometres/miles (distance) of physical activity (e.g. walking, running, swimming, bicycle) are needed to burn off the corresponding energy [13]. PACE might be easier to understand compared to other nutritional labels because consumers do not need health literacy or have advanced numeracy skills to understand PACE [14]. However, in a recent study, Antonelli & Viera (2015) showed a stronger effect of PACE among people of higher compared to lower SEP, in particular among richer people [15].

The food choices of people of higher SEP are more motivated by health than those of people of lower SEP [16]. As information-based interventions typically rely on people being motivated by health in their food choices [17], the presence of nutritional labels may lead to healthier eating behaviours primarily among people of higher SEP.

2. OBJECTIVES, OUTCOMES MEASURES AND HYPOTHESES

OBJECTIVES	OUTCOME MEASURES	HYPOTHESES

Primary objective
 
To investigate the effect of labelling (kcal or PACE) on the total self-served energy among participants of lower and higher SEP.
	
Total self-served energy in kcal from hypothetical meals
	
Labelling (kcal or PACE) will influence the size of self-served portion and result in reduced total self-served energy among both participants of lower and higher SEP.
 
Kcal and PACE labelling will exert a stronger effect on self-served energy among participants of higher compared to lower SEP.

		PACE labelling will exert a stronger effect on self-served energy than kcal labelling.
Secondary objectives To investigate the psychological processes that may explain the different effect of the intervention and whether health motivation and physical activity level mediate the differential effect of labelling (kcal or PACE) on total self-served energy among participants of lower and higher SEP.	Executive function (tasks) Health motivation in food choices (questionnaire)	Participants of higher SEP will have better executive function than participants of lower SEP, which will moderate the relationship between SEP and the effect of energy/PACE labelling on the total energy of the selected meal. Kcal/PACE labelling will exert a stronger effect on self-served energy among participants of higher SEP because they will be more motivated by health in their food choices than participants of lower SEP.

3. EXPERIMENTAL DESIGN

Participants will take part in an online survey. They will be asked to choose the amount of food they would like to eat based on pictures of 18 dishes sequentially displayed on the screen. They will be randomly allocated to four different groups: kcal labelling, PACE labelling (minutes to walk to burn off the calories), kcal and PACE labelling combined, no labelling, in a between subject design.

4. PARTICIPANTS AND RECRUITMENT

4.1. Recruitment

Participants will be recruited through Prolific, an online recruitment platform in which participants are compensated proportionate to the time it takes to complete the online study ($\approx 5\text{£}/\text{hour}$ reward participants). Participants' recruitment will be stratified by gender (50% male, 50% female), student status (3.5% yes and 96.5% no) [18] and qualification levels (50% A level or below, 50% above A level) in order to recruit participants of lower and higher SEP.

4.2. Inclusion criteria

- UK residents, age ≥ 18
- Fluent in English
- Have access to a computer and Internet

4.3. Exclusion criteria

- Having any dietary restriction:
 - Vegetarian
 - Vegan

- Gluten-free
- Sugar-free
- Diary/lactose-free
- Food allergy (e.g. milk, eggs, nut, wheat, fish, etc.)

- Taking part more than once:
Prolific is designed to avoid the same participant to take the same survey twice (i.e., one participant cannot access the study link twice). Each participant recruited on Prolific has a unique ID. If for some reasons a participant takes the survey twice, we will delete the second submission from the dataset by checking the ID duplicates. For the same reason, to avoid one participant takes the survey twice with different accounts, we will delete the second submission from the dataset by checking the IP duplicates.
- Failing an attention check (**Appendix G, item 9; Appendix H, item 10; Appendix O, item 4**).
- Completing the main task too fast, i.e., less than 2 sec per dish = less than 36 sec in total, that will be interpreted as careless or insufficient effort responding [19], [20].

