5. METHODS

5.1. Portion selection task

Procedure

Participants will be randomly allocated to one of the following groups:

- kcal labelling (*kcal+/PACE-*);
- PACE labelling (*kcal-/PACE+*);
- kcal and PACE labelling (*kcal+/PACE+*);
- no labelling (*kcal-/PACE-*).

They will be asked to choose the amount of food they would like to eat in 18 hypothetical meals sequentially displayed on the screen. The first picture of each dish will show 20 kcal of this dish on a white plate. Participants will be able to virtually 'serve themselves' the amount of food they would like to eat by increasing or reducing the quantity on the plate using the arrow keys on their keyboard (to increase = right key; to decrease = left key). Energy content will increase by 20 kcal each time they will tap the right arrow key (max. 1000 kcal). Participants will have to increase the portion size at least once (i.e., at least one tap on the right arrow key) to be able to confirm their choice using the spacebar. The 18 dishes will be randomised in order.

Foods

The food stimuli are based on a previously published work by Whitelock et al. (2018) (**Appendix A**). For each dish, 50 pictures have been taken to reflect the increase in portion size. The number of calories increases 20 kcal by 20 kcal from a minimum of 20 kcal (first picture) to a maximum of 1000 kcal (50th picture) [21].

Interventions

For each portion and dish, participants will see on the screen a label showing the number of calories, physical activity calories equivalent or both. Labels are adapted from Swartz et al., 2013 [22].

Kcal labelling (kcal+/PACE-)

500 kcal

Participants allocated to this group will see on the screen the amount of food increasing or decreasing based on how many times they tap on the corresponding keys and a real-time kcal counter synchronised with the food amount changes (i.e., increasing/decreasing).

PACE labelling (kcal-/PACE+)

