17. APPENDIX H: MEAL CHOICE TASK INSTRUCTIONS

Kcal-/PACE- group

Before the task begins

Portion selection task

In this task, you will be shown pictures of 18 different dishes. For each dish, you will be asked to decide how much you would like to eat as if you were eating it as main meal.

You can change the quantity using the arrow keys on your keyboard:

- tap on the right arrow to increase the quantity, on the left one to decrease the quantity
- use the space bar to select the portion size you would like to eat.

Before you make your choice, take the time to explore the full range of portion sizes.

You need to increase the amount of food at least once to be able to select a portion and continue.

Tap the spacebar to start.

During the task

How much would you like to eat?

[figure not shown]

*Use the arrow keys to change the portion size.
Use the spacebar to select the amount you would like to eat.*

Kcal+/PACE- group:

Before the task begins

Portion selection task

In this task, you will be shown pictures of 18 different dishes. For each dish, you will be asked to decide how much you would like to eat as if you were eating it as main meal. For each portion, the label on the left will show you the calorie content.

You can change the quantity using the arrow keys on your keyboard:

- tap on the right arrow to increase the quantity, on the left one to decrease the quantity
- use the space bar to select the portion size you would like to eat.

Before you make your choice, take the time to explore the full range of portion sizes.

You need to increase the amount of food at least once to be able to select a portion and continue.

Tap the spacebar to start.

During the task

How much would you like to eat?

500 kcal

[figure not shown]
*Use the arrow keys to change the portion size.
Use the spacebar to select the amount you would like to eat.*

On average women need 2,000 kcal per day and men need 2,500 kcal per day.

Kcal-/PACE+ group:

Before the task begins

Portion selection task

In this task, you will be shown pictures of 18 different dishes. For each dish, you will be asked to decide how much you would like to eat as if you were eating it as main meal. For each portion, the label on the left will show you the physical activity calorie equivalent, as the number of minutes of walking needed to burn off the calories in the meal.

You can change the quantity using the arrow keys on your keyboard:

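### The too-fast exclusion acts after label exposure and is linked to the outcome: at ordinary tapping speeds only participants with small mean portions can fail it, and no planned analysis restores them

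*Combined protocol and SAP*

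**What the plan says.** Section 4.3 (Exclusion criteria) removes participants for "Completing the main task too fast, i.e., less than 2 sec per dish = less than 36 sec in total", a speed "that will be interpreted as careless or insufficient effort responding".

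The timed task is described in section 5.1. Participants "choose the amount of food they would like to eat in 18 hypothetical meals". On the starting point: "The first picture of each dish will show 20 kcal of this dish on a white plate". On the response: "Energy content will increase by 20 kcal each time they will tap the right arrow key (max. 1000 kcal". On the minimum action: "Participants will have to increase the portion size at least once". In the kcal arm the screen carries "a real-time kcal counter synchronised with the food amount changes", and the PACE and combined arms have equivalent counters.

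Appendix H gives the same advice in all four arms: "Before you make your choice, take the time to explore the full range of portion sizes". The software enforces one tap only.

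In section 6, randomisation comes before the meal task. Section 7.2 leaves ineligible submissions unanalysed, and section 7.9 keeps recruiting until 1,600 analysable participants are reached. None of the four sensitivity analyses in section 7.6 brings speed-excluded participants back.

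**The concern.** Self-served energy on a dish is a count of net taps, and the speed limit is set on the time taken to make those taps. A careless participant who taps up to large portions will pass. An equally quick participant who stops at small portions can fail. So the rule tracks the size of the answer as well as the effort behind it.

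Section 2 expects labels to reduce portions, more so in higher SEP. Exclusion can therefore depend on both arm and outcome, and may differ by education group. That would disturb the label contrasts and possibly the label-by-education interaction. Smaller portions in the label arms would put more of those participants under the limit and pull the contrasts towards zero. Time spent reading the label would protect label-arm participants from exclusion and push the other way. The plan has no by-arm count and no comparison analysis that would show which is happening.

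**Working it through.** **1. The plan's figure.** 18 dishes × 2 s = 36 s. It reproduces.

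**2. Taps needed** (section 5.1). Net taps = (portion − 20)/20: 1 for 40 kcal, 14 for 300, 24 for 500, 29 for 600, 49 for 1000. Finishing in 2 s with no looking time needs 14/2 = 7 taps per second for 300 kcal, 24/2 = 12 for 500 and 29/2 = 14.5 for 600.

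**3. Largest mean portion that can fall under the limit.** Portion = 20 + 20 × rate × (2 − looking time). Tap rate and looking time are assumptions, because the documents give neither.

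| Taps per second | No looking time | 0.5 s | 1.0 s |
|---|---|---|---|
| 5 | 220 kcal | 170 kcal | 120 kcal |
| 7 | 300 kcal | 230 kcal | 160 kcal |
| 10 | 420 kcal | 320 kcal | 220 kcal |

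If holding the key repeats the step at, say, 30 per second, the ceiling with no looking time is 20 + 20 × 30 × 2 = 1220 kcal, above the 1000 kcal maximum. The restriction to low portions then largely disappears.

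**4. Participants who explore.** Reaching the top takes 49 taps, or 4.9 s at 10 per second, so a fully explored dish is over the limit whatever portion follows. They then tap back: 49 + 20 = 69 taps to settle on 600 kcal, and 49 + 40 = 89 to settle on 200 kcal. For them a larger choice takes less time.

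**5. Simulation.** 40,000 per arm; 18 dishes; portions clipped to 40–1000 kcal; within-person SD 300 (section 7.9); between-person SD 300 (section 7.9) or 150; label effect 8%. Assumed: median tap rate 5, 7 or 10 per second; median looking time 0.5, 1.0 or 1.5 s; control mean 500, 600 or 763 kcal before clipping. The 763 is the control mean at which the plan's 8% and 80% power agree: SD of an 18-dish mean = √(300² + 300²/18) = 308.2, which with 400 per arm gives a detectable difference of 61 kcal, and 61/0.08 ≈ 763.

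With between-person SD 300 and no exploration:
- Excluded participants average about 95–280 kcal, kept participants about 490–730 kcal.
- Exclusion is 0.3–25% of controls and 0.5–29% of a label arm (0–14% and 0–19% with between-person SD 150).
- Of participants averaging below 200 kcal, 15–97% are removed; the rest stay in.

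Tap rates vary around the median, so some simulated participants exceed the table's ceilings. With between-person SD 150 and a median of 10 taps per second, the excluded average reached 444 kcal in one setting, against 722 kcal for those kept.

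Effect on the label contrast, full sample to analysed sample (between-person SD 300; control mean 500, 7 taps per second and 0.5 s unless stated):
- No exploration: 28.7 to 20.7 kcal, a fall of 8.0.
- No exploration, control mean 763, looking time 1.0 s: 43.4 to 39.5 kcal, a fall of 3.9.
- Half explore: 30.2 to 26.8 kcal, a fall of 3.4 (7.0% of controls and 8.5% of the label arm excluded).
- 90% explore: 31.4 to 30.4 kcal, a fall of 1.0 (1.4% and 1.8%).
- No exploration, label reading adds 0.3 s per dish: 29.3 to 38.6 kcal, a rise of 9.3 (14.3% and 12.1%).

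Full-sample values differ between runs with the same portion settings through simulation error; the shift within a run is what matters.

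**6. Dependence on the exclusion ratio.** Suppose control and label means of 600 and 552 kcal (8% lower) and an excluded mean of 250 kcal. Shrinkage = pL × 302/(1 − pL) − pC × 350/(1 − pC), where pL and pC are the proportions excluded in the label and control arms. With 2% in the label arm and 1% in control it is 6.2 − 3.5 = 2.6 kcal before rounding of terms; with 6% and 3% it is 19.3 − 10.8 = 8.5 kcal. With 2% in both it is 6.2 − 7.1 = −1.0 kcal, so the contrast widens slightly. Shrinkage needs an exclusion odds ratio above 350/302 = 1.16.

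**The case against.** The rule is pre-specified, objective and identical in all arms. Every arm is told to explore the full range, so a participant who averages under 2 seconds at ordinary tapping speeds has ignored that advice on most dishes, which is close to the low effort the rule is meant to catch. This stands, and it limits the problem: the more participants explore, the less the rule matters. It does not remove it, because exploration is not enforced and its uptake is unknown.

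The larger simulated shifts also come from harsh settings. The 8.0 kcal fall and the 9.3 kcal rise share control-arm settings under which about 14% of controls fail on speed alone, more than the roughly 10% that section 7.9 allows for all losses. They show how the rule can act and are not forecasts.

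Section 7.2 promises to report withdrawals made afterwards, with reasons. That may cover speed exclusions, so it would be too strong to say the plan hides them. It does not promise counts by arm, and no analysis shows what the exclusions do to the result.

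**Conclusion.** The concern holds in a limited form. The exclusion is made after randomisation and exposure, it is linked to the primary outcome by the design of the task, and no sensitivity analysis covers it. At single-tap speeds up to about 10 per second, only participants with mean portions below roughly 120 to 420 kcal can fail, depending on tap rate and looking time.

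A reader might go further in two ways that the documents do not support. One is to call the rule in effect a cut on the primary outcome. It is not: too fast implies a small mean portion at these speeds, but a small mean portion does not imply too fast. The other is to conclude that the label effect is diluted by 5 to 18% (2.6 to 8.5 of 48 kcal in step 6). That range rests on an assumed 2:1 ratio of exclusions, label to control, which appears nowhere in the plan.

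Size and direction remain unknown. They depend on tap rate, looking time, control mean, uptake of exploration and whether a held key repeats, none of which the documents give. If most participants explore, the shift is about 1 kcal. This is a cheap safeguard and not a serious flaw.

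**What to change.** Keep the rule for the main analysis and make two additions.

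1. In section 7.6, add one sensitivity run of the main model that also includes participants removed only for speed, provided they passed the attention checks and otherwise meet eligibility.
2. Report the number excluded for speed by arm and by education group.

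This needs a few lines of SAP wording, retention of the excluded records and one extra model run. The downside is that some careless responders enter the sensitivity set, so it should be read beside the main result and not replace it.

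A criterion based on time net of tapping would weaken the tie to portion size. It is optional and possible only if such timing is recorded: section 6 does not list keystroke timing among the contents of the result files. A rule based on making exactly one tap on nearly all dishes should not be adopted, because one tap is 20 + 20 = 40 kcal and the rule would itself be a cut on the outcome.

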5. METHODS

5.1. Portion selection task

Procedure

Participants will be randomly allocated to one of the following groups:

- kcal labelling (*kcal+/PACE-*);
- PACE labelling (*kcal-/PACE+*);
- kcal and PACE labelling (*kcal+/PACE+*);
- no labelling (*kcal-/PACE-*).

They will be asked to choose the amount of food they would like to eat in 18 hypothetical meals sequentially displayed on the screen. The first picture of each dish will show 20 kcal of this dish on a white plate. Participants will be able to virtually 'serve themselves' the amount of food they would like to eat by increasing or reducing the quantity on the plate using the arrow keys on their keyboard (to increase = right key; to decrease = left key). Energy content will increase by 20 kcal each time they will tap the right arrow key (max. 1000 kcal). Participants will have to increase the portion size at least once (i.e., at least one tap on the right arrow key) to be able to confirm their choice using the spacebar. The 18 dishes will be randomised in order.

Foods

The food stimuli are based on a previously published work by Whitelock et al. (2018) (**Appendix A**). For each dish, 50 pictures have been taken to reflect the increase in portion size. The number of calories increases 20 kcal by 20 kcal from a minimum of 20 kcal (first picture) to a maximum of 1000 kcal (50th picture) [21].

Interventions

For each portion and dish, participants will see on the screen a label showing the number of calories, physical activity calories equivalent or both. Labels are adapted from Swartz et al., 2013 [22].

Kcal labelling (kcal+/PACE-)

500 kcal

Participants allocated to this group will see on the screen the amount of food increasing or decreasing based on how many times they tap on the corresponding keys and a real-time kcal counter synchronised with the food amount changes (i.e., increasing/decreasing).

PACE labelling (kcal-/PACE+)

 **100 min**

Participants allocated to this group will see on the screen the amount of food increasing or decreasing based on how many times they tap on the corresponding keys and a real-time PACE counter (as minutes needed to walk to burn off the calories) synchronised to the food amount changes (i.e., increasing/decreasing) with 4 min being equivalent to 20 kcal [13].

Kcal and PACE labelling (kcal+/PACE+)

500 kcal

 **100 min**

Participants allocated to this group will see on the screen the amount of food increasing or decreasing based on how many times they tap on the corresponding keys and a real-time kcal and PACE counters synchronised to the food amount changes (i.e., increasing/decreasing).

No labelling (kcal-/PACE-)

Participants allocated to this group will only see on the screen the amount of food increasing or decreasing based how many times they tap on the corresponding keys.

5.2. Measures of socioeconomic position

Five measures of socioeconomic status will be included. Participants will be asked to report:

- their highest educational qualification;
- their number of years in higher education;
- their current employment status;
- their household income and their household composition;
- a subjective measure of their socioeconomic position using the MacArthur Scale of Subjective Social Status (SSS) [23].

5.3. Measures of executive functions (EF)

Cognitive measures of EF

Inhibition is the ability to suppress impulsive or automatic responses (e.g., not choosing unhealthy foods). A Stroop task will be used to measure inhibition ($\approx 2\text{min.}30\text{sec.}$). In this task, participants are given colour words written in colour and are asked to indicate the colour of the word (not its meaning) by key press as fast as they can without making too many errors. The task included three types of trials:

- Congruent trials: colour word and the colour it is presented in are the same;
- Incongruent trials: colour word and the colour it is presented in are not the same;
- Control trials: coloured rectangles.

The task includes 4 colours (red, green, blue, black) \times 3 colour-stimuli congruency (congruent, incongruent, control) \times 7 repetitions = 84 trials randomly sampled.

Working memory is the ability to monitor the relevance of incoming stimuli and update information in memory as required and is implied in goal-shielding (e.g., stick to healthy eating goals). A backwards digit-span task will be used to measure working memory (≈ 7 min.). This task will require participants to repeat series of digits of increasing length in the reversed order. Depending on performance, participants move up a level or down a level. The first trial is a sequence of two visual digits. Assessment is 14 trials in total.

